Radiotherapy (RT) is the mainstay of treatment for patients with brain metastases¹, with a shift over the past two decades from whole brain radiotherapy (WBRT), which treats the entire brain, to focal stereotactic radiosurgery (SRS) for patients with a limited number or volume of tumors^{2,21,22}. Randomized trials have shown that WBRT provides no survival benefit over SRS for these patients¹. SRS targets the metastases alone with high, ablative doses of radiotherapy, most commonly in a single treatment, with minimal interruptions to systemic therapy schedules.

The challenge of radiation-induced cognitive decline. While radiotherapy is indispensable for the management of intracranial tumors, it is associated with an inevitable decline in neurocognitive function in up to 90% of patients who survive more than 6 months after treatment²³. This manifests with changes in verbal and nonverbal memory, language and semantic processing, attention and processing speed, and/or executive functioning, and can be devastating for patients and their quality of life. Neurocognitive outcome is increasingly being recognized as a primary endpoint in brain tumor clinical trials, next to tumor control and patient survival^{7,24,25}. WBRT is notorious for significant post-treatment cognitive decline, and cognitive-sparing therapies that have been explored on WBRT trials include hippocampal-avoidance^{7,25-27} and the addition of medications like memantine (N-methyl-D-aspartate receptor blocker)²⁸ or donepezil²⁹.

A recent landmark phase III randomized controlled trial, Alliance study N0574, compared SRS alone vs. SRS + WBRT for patients with limited (1 to 3) brain metastases, with neurocognitive decline as the primary outcome⁵. The rate of cognitive deterioration at 3 months after treatment was significantly higher in the SRS + WBRT arm (91.7% vs. 63.5%), establishing SRS alone as the less toxic option and reflecting a general consensus in treatment strategy for limited brain disease^{1,2,22}. Yet the most striking result from this trial was the **high rate of cognitive deterioration (nearly 64% at 3 months) with SRS alone**. Another Alliance trial, N107C, which randomized patients with a resected brain metastasis to SRS vs. WBRT showed 52% cognitive deterioration at 6 months after SRS alone⁸. Clearly SRS is an improvement over WBRT for neurocognition, but the post-treatment cognitive outcomes are still dismal with standard SRS.

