3. Research Plan

We will prospectively enroll 60 adult patients with 1-3 brain metastases who are eligible for treatment with intracranial stereotactic radiosurgery (SRS) at UC San Diego(UCSD)/Moore's Cancer Center.

Inclusion criteria include: age ≥ 18 ; Eastern Cooperative Oncology Group (ECOG) performance status of 0-2 (score of 0, no symptoms; 1, mild symptoms; 2, symptomatic, $< 50\%$ in bed during the day); pathologic confirmation of extra-cerebral tumor site (i.e. breast, lung, melanoma); ability to answer questions and follow commands via neurocognitive testing; estimated life expectancy > 6 months.

Exclusion criteria include: inability to undergo MRI with contrast, prior WBRT, ineligibility for brain SRS (i.e. leptomeningeal metastases; metastases from lung small cell carcinoma or primary CNS lymphoma), ineligibility for cognitive-sparing (tumor infiltrating hippocampus or critical white matter (WM) tracts). Concurrent chemotherapy with brain SRS is not allowed on study. These criteria closely follow the Alliance Trial N0574⁵, given that the cognitive deterioration rate from their standard SRS arm will be used as historical controls to power the current trial. Patient and tumor-specific variables including age, sex, race/ethnicity, educational status, occupation, primary tumor histology, systemic therapy, use of steroids and anti-epileptic drugs, tumor number, tumor size and tumor location, will be prospectively recorded.

The study protocol and timeline for each patient is shown in Figure 1 below. Patients will undergo MR imaging with DTI and 3D volumetric imaging at baseline (pre-SRS), and 1 month, 3 months, and 6 months afterwards. This regimen of post-SRS MR imaging is clinical standard of care². Segmentation of critical white matter and hippocampal volumes will be performed pre-SRS for use in brain SRS planning. Formal neurocognitive assessments will be performed at baseline and 3 months post-SRS⁵.

[figure not shown]

Figure 1. Timeline of consent, MRIs, Neurocognitive (NC) assessments, SRS planning and Delivery, and Follow-ups. WM=White matter; HC=Hippocampus.

Recruitment

Subjects will include those patients seen at UC San Diego/Moore's Cancer Center. A study coordinator will screen for eligible adult patients with brain metastases. They will review the patient's medical record and determine if they would be a candidate for the study. The principal investigator will be notified of subject eligibility and consult

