Patients will be seen by the treating physician on the day of SRS, and on subsequent follow-up visits. They will be followed closely with clinical and imaging exams for safety and tumor recurrence (i.e., 1 month, 3 months, 6 months post-SRS). All treatment-related toxic effects and adverse events will be recorded according to NCI Common Terminology Criteria for Adverse Events, version 4.0. Local tumor control rates for each treated lesion will be assessed according to the revised Response Assessment in Neuro-oncology (RANO) criteria^{81,82}.

Payment

Parking for study patients related to study visits will be complementary. Subjects will be compensated \$100 for participation in this study to help compensate for time and travel costs.

Statistical Considerations

Primary Objective Analysis:

Cognitive test results (pre- and post-SRS) will be scored based on standardized published norms^{72,87}. Cognitive deterioration will be defined as a decline of greater than 1 SD on at least 1 of the 7 cognitive tests (Table 2, not including BDI or FACT-BR). Fisher's exact 2-group binomial test will be used to compare the proportion of patients with 3-month post-SRS cognitive deterioration between the current cognitive-sparing SRS study and previously reported with standard SRS.⁵ Further analyses of pre- to post-SRS cognitive change for each test will

utilize a reliable change index (RCI)⁸⁷. This index is derived from the standard error of measurement of each test, and it represents the 90% confidence interval (CI) for the difference in raw scores from baseline to follow-up that is expected if no real change has occurred. RCI values below the 90% CI are indicative of significant decline. RCIs also account for practice effects, which is ideal for this study where evaluations are 3 months apart. One-sample t-tests ($H_0=0$) will be used to determine significant group decline in RCIs by test and cognitive domain. Pearson correlation coefficients will be used to assess associations between RCIs and depression scores. Bonferroni corrections will be applied to control for Type I errors due to multiple comparisons.

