With RCI at 3-months post-SRS as the outcome variable, linear regression modeling will be used to analyze patient-specific (e.g. age, sex), tumor-specific (e.g. histology, number of lesions, imaging progression), and treatment-specific (e.g. previous chemotherapy, anti-epileptic drugs) predictors of neurocognitive change after cognitive-sparing SRS. Model selection will be based on Akaike Information Criterion (AIC)^{88,89}. Given the small sample size and multiple variables of interest, this will be an exploratory analysis. Given that cognitive-sparing on this study will not be performed at the sacrifice of tumor coverage, we expect the overall local control and survival rates in the cohort to be comparable to those in other studies of SRS alone for patients with 1-3 brain metastases^{1,5,6,22}. Treated tumor local control rates will be assessed at 3- and 6-months post-SRS. Local tumor control of each treated lesion will be assessed with modified RANO criteria⁸⁴ where tumor progression is defined as >25% increase in the size of a treated lesion. Tumor progression of treated metastases will be evaluated independently of the development of new lesions⁵. Local tumor control rate at 6 months and overall survival rate (death from any cause) at 12 months will be compared to historical values⁵ using a 1-sample t-test.

Secondary Objective Analyses

The imaging biomarker of each structure (mean white matter diffusivity metrics and hippocampal volume) will be modeled as a function of time using linear mixed effect models^{13,16}. These models are well-suited for longitudinal analysis since they account for within-subject correlation between repeated measures, and allow for incomplete outcome data. Individual structures will be classified based on whether they received greater or less than the median dose for that structure across all patients. The interaction of dose and time will be tested within the model to assess whether dose mediates longitudinal trends. In addition, potential fixed-effect covariates will be selected from a list of patient and tumor-specific variables, such as age, sex, tumor size and location. Model selection will be based on AIC. To account for correlated observations within subjects, patient-specific random intercepts and time-associated slopes will be tested.

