Sample Size Determination: This study is powered based on the endpoint of cognitive deterioration at 3 months post-SRS, defined as decline of greater than 1 standard deviation (SD) from baseline on at least 1 of the neurocognitive tests. This was the primary endpoint of the Alliance N0574 study. With 60 accrued patients

and assuming a 20% drop-out rate, we will have sample size $n=48$. We have 85% power to detect a change in the cognitive deterioration rate from 64% in standard SRS to 42.5% in the current cognitive-sparing study with $n=48$ (Fisher's exact 2-group binomial test, 2-tailed $\alpha=0.05$).

4. Risks

The anticipated risk to patients in this study is minimal.

The MRI scans to be obtained at baseline would be added on to the same scan performed for routine SRS planning for patients. Follow up MRI would be standard of care imaging and would be obtained regardless of whether the patient is on or off study. These scans do not involve any radiation exposure. There are no additional risks associated with the research scans aside from discomfort due to the additional 8-10 minutes of scan time required. However, these scans are frequently performed as part of standard of care during presurgical planning without adverse effects. Some patients may experience claustrophobia in the MR scanner and may require the use of medications for this, as is prescribed routinely for brain MRIs when indicated.

Intracranial SRS would be performed identically to standard of care, except for adding additional regional avoidance for cognitive sparing. In cases where sparing of these structures cannot be performed without sacrificing treatment of the tumor or another critical structure, this will be recorded and the default will be the standard clinical plan. While clinical benchmarks of SRS quality will not be sacrificed on this study, there is a possibility that changing the SRS plan to achieve cognitive sparing may change the dose distribution to other structures in the brain. It is unclear whether this would change any clinical outcomes since SRS plans must adhere to the same rigorous standards as the current standard of care.

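### The stated 85% power does not follow from a two-group Fisher's exact test with n=48, and the size of the historical group it depends on is not given

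*Protocol*

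**What the plan says.** Under Sample Size Determination (Protocol, section 3, Statistical Considerations), enrolment is 60 and a 20% loss leaves 48 evaluable patients. The paragraph then states: "We have 85% power to detect a change in the cognitive deterioration rate from 64% in standard SRS to 42.5" per cent. In parentheses it gives the basis: "Fisher's exact 2-group binomial test, 2-tailed", with alpha 0.05.

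The Primary Objective Analysis names the same procedure: "Fisher's exact 2-group binomial test will be used to compare the proportion of patients with 3-month post-SRS cognitive deterioration", the comparator being the rate previously reported for standard SRS.

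The comparator is identified in two other places. Section 2 reports the 3-month deterioration rate in the cited trial as "significantly higher in the SRS + WBRT arm (91.7% vs. 63.5" per cent, so the SRS-alone figure is 63.5%, rounded to 64% for the power statement. Section 3 explains that its eligibility criteria follow that trial closely, "given that the cognitive deterioration rate from their standard SRS arm will be used as historical controls to power the current trial". The protocol nowhere gives the number of patients in that SRS arm or the number assessed at 3 months.

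**The concern.** A two-group test compares two observed proportions and carries the sampling error of both. Its power cannot be computed from one group size, yet one is all the protocol supplies. If the 48 is read as a per-group figure, power is far below 85%. If the historical group is some other size, the reader is not told which.

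This is the protocol's only power statement and its only statistical justification for enrolling 60 patients. The study has a single arm, so its main conclusion rests on this comparison. The stated 85% means a 15% chance of missing the target effect. Under the test as named, that chance would be 34.9% with 100 historical patients (100 − 65.1) and 51.2% with 48 (100 − 48.8). A non-significant result would then be read as stronger evidence against cognitive sparing than it is.

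**Working it through.** **Inputs from the protocol**
- New cohort: 60 × (1 − 0.20) = 48 evaluable. This step is correct.
- Rates: 0.64 for standard SRS (0.635 in section 2) and 0.425 for the new cohort.
- Test: two-sided, two-group Fisher's exact, alpha 0.05.
- Historical group size m: not given. It is treated below as an assumption and varied.

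**Step 1: the stated figure under the named test**

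Exact power = Σₓ Σᵧ Bin(x; 48, 0.425) · Bin(y; m, 0.64) · 1[p(x, y) ≤ 0.05].

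Here p(x, y) is the two-sided Fisher p-value, the sum over tables no more probable than the one observed. The last column is the new-cohort rate at which power reaches 85%.

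| Assumed m | Power at 42.5% | Rate detectable with 85% power |
|---|---|---|
| 48 | 48.8% | 32.1% |
| 60 | 55.6% | 33.9% |
| 100 | 65.1% | 36.7% |
| 200 | 74.8% | 39.5% |
| 500 | 81.0% | 41.3% |
| 1,000 | 83.9% | 42.1% |
| 2,000 | 84.9% | 42.4% |

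Power first reaches 80% at about m = 420 (79.6% at 400, 80.2% at 420). Among the sizes computed up to 100,000, the highest power is 84.96%, at 7,500; at 100,000 it is 83.9%. The test is discrete, so power does not rise smoothly with m.

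A normal approximation for 48 versus 48 gives the same message. The pooled rate is (0.64 + 0.425)/2 = 0.5325.
- Null SE = √(2 × 0.5325 × 0.4675/48) = 0.1018.
- Alternative SE = √((0.64 × 0.36 + 0.425 × 0.575)/48) = 0.0995.
- Power = Φ((0.215 − 1.96 × 0.1018)/0.0995) = 56.1%.

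Using 63.5% in place of 64% lowers the exact figure for 48 versus 48 to 46.8%.

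**Step 2: a calculation that does give about 85%**

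Treat the historical rate as a known constant and use a one-sample normal approximation with n = 48. The alternative SE is √(0.425 × 0.575/48) = 0.07135.
- Against 64%, alternative variance: Φ(0.215/0.07135 − 1.96) = Φ(1.053) = 85.4%.
- Against 63.5%, null variance: null SE = √(0.635 × 0.365/48) = 0.06949, and Φ((0.21 − 1.96 × 0.06949)/0.07135) = Φ(1.034) = 85.0%.
- Against 64%, arcsine: 85.3%.

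Two other variants lie further off: 86.7% (64%, null variance) and 83.7% (63.5%, alternative variance). The stated figure therefore resembles a one-sample calculation. That origin is an inference; the protocol does not state it.

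**Step 3: the exact test for a fixed rate**

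Use a one-sample exact binomial test with n = 48 and 0.025 in the lower tail.
- P(X ≤ 23) = 0.0164 at 64% and 0.0196 at 63.5%.
- P(X ≤ 24) = 0.0325 at 64% and 0.0383 at 63.5%, both above 0.025.

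The rule is to reject at 23 or fewer of 48. Power at 42.5% is P(X ≤ 23) = 81.8%, and 85% power needs a true rate of about 41.5%.

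**The case against.** **The figure is unsupported, not impossible.** With 2,000 historical patients the power is 84.9%, which rounds to 85%. This stands: no size is stated, so a very large group cannot be ruled out from the text. But nothing in the protocol suggests a group of that size, and a reader still cannot derive 85% without assuming one.

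**The comparator is traceable through the citation.** The intended arm is identified, and its exact counts could be set out in an analysis plan. This is fair as to where the counts are recorded, and it is why only a range is shown here. It does not rescue a power figure that the protocol itself states and attributes to a specific test.

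**The one-sample origin is speculative.** Agreed, and the conclusion does not need it. The protocol's later statement, "Local tumor control rate at 6 months and overall survival rate (death from any cause) at 12 months will be compared to historical values" by a one-sample test, can be read either way. It may show that historical values were generally treated as fixed, or that the authors distinguished the two designs and meant two groups for the primary endpoint.

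**The figures depend on conventions.** True, but for Fisher's test the alternative convention does not help the plan. With doubled one-tail p-values, power is 62.9% at 100 historical patients, 80.5% at 1,000 and 81.4% at 2,000. The one-sample figure is sensitive to discreteness: against 64%, 24 of 48 has a two-sided p of 0.0503 by the probability-ordering method, just outside rejection. Counting it would give 88.4% power at the price of exceeding 5%.

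**It may be only a mislabelled test costing about 3 points.** If a fixed-rate comparison was meant, that is correct (85% against 81.8%). But the same label governs the planned primary analysis. Run as written, that analysis would carry the historical group's sampling error, which a one-sample power figure leaves out.

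**Conclusion.** The concern holds. The named test, the single sample size and the stated 85% do not fit together. Under the two-group Fisher's test, power is below 80% for a historical group of about 400 or fewer and about 49% if the groups are equal; it rounds to 85% only from about 2,000. Under a fixed-rate reading, the test is misnamed in both paragraphs and its exact power is about 82%.

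These results rest on the protocol's rates (64% and 42.5%), 48 evaluable patients, two-sided alpha 0.05 and, for the two-group figures, an assumed historical size and the probability-ordered Fisher p-value. The actual shortfall under the two-group test cannot be fixed from this document because the historical count is absent. The correction is needed because the trial's only power figure is affected.

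**What to change.** Amend the Primary Objective Analysis and Sample Size Determination paragraphs so that both describe the same comparison, by one of two routes.

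1. **Keep the two-group Fisher's exact test.** State the historical numerator and denominator to be used. Replace 85% with the exact power at that size, or give the new-cohort rate detectable with 85% power.
2. **Name a one-sample exact binomial test against the fixed historical rate in both paragraphs.** State which rate (63.5% or 64%; the cut-off is the same), the rule of rejecting at 23 or fewer of 48, and power of about 82%. Add that this treats the historical rate as known and ignores its sampling error.

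Either route is a wording change and requires no added patients in itself. The cost is a less favourable stated power. Under route 1 with a modest historical group, the sponsor should also say whether the restated power is acceptable for 60 enrolled patients, since correcting the figure does not settle that question.
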